
credentialed Qualtrics links provided to them by the study staff. Our study staff is experienced in implementing Qualtrics surveys remotely in prior studies and has extensive experience providing brief intervention for caffeine reduction using the manual-only approach. These data will support feasibility and initial efficacy of future randomized controlled trials in populations experiencing specific caffeine-related problems.

2. Objectives (include all primary and secondary objectives)

Primary objective. Determine to what extent participants will engage with a remote caffeine reduction intervention for caffeine-related problems and find it acceptable.

Secondary objective (a). Determine to what extent participants are successfully able to reduce their caffeine consumption following the remote intervention.

Secondary objective (b). Determine to what extent participants report improvement in common caffeine-related problems (e.g., insomnia, anxiety, gastrointestinal distress) following the remote intervention.

Secondary objective (c). Determine whether participants randomized to the immediate intervention group (at 7-weeks post enrollment and post-treatment) show greater caffeine reductions or greater improvements in caffeine-related problems relative to the delayed treatment group at 7-weeks post-enrollment (prior to delayed treatment). This randomization will allow us to compare the initial efficacy of our intervention with caffeine reductions that may occur spontaneously over the same duration.

3. Background (briefly describe pre-clinical and clinical data, current experience with procedures, drug or device, and any other relevant information to justify the research)

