during the call. Study staff will also use video whenever possible. The study staff will use the Zoom chat function or email to send the participant survey links and will verbally instruct them on how to complete the surveys, beginning with the consent survey. The oral consent form document will be embedded within the Qualtrics survey such that the participant can download the consent form document, or alternatively may be emailed to the participant. The study staff will ask the participant to read aloud the first part of the consent form in order to confirm that they were able to download the document and are able to read English fluently. Then the participant will be provided the opportunity to review the document and ask the study staff any questions they have about participation. This will be followed by a consent quiz administered via Qualtrics survey link. Participants will provide oral consent and answer all of the consent quiz questions correctly prior to proceeding with the remaining screening questionnaires. Following consent, participants will complete standardized medical/substance use history questionnaires as well as surveys to determine their caffeine/cigarette use, caffeine-related problems, and standardized assessments of anxiety, sleep, and gastrointestinal problems as outlined in Table 1. The participant will fill out the surveys via Qualtrics links, or the study staff will interview them and enter their responses on the study staff computers. Study staff will provide instructions to guide them through the assessment completions, review their responses on Qualtrics, and may ask follow-up questions if necessary, to supplement their survey responses. After determining eligibility, participants will be randomized to either the Immediate or Delayed treatment group using an urn randomization procedure accounting for caffeine consumption, age, and sex as was utilized in prior research in our laboratory (Evatt et al., 2016; Sweeney et al., 2019).

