There will be no anticipated disruption to any ongoing treatment or routine care.

- f. Justification for inclusion of a placebo or non-treatment group.

There will be no anticipated placebo or non-treatment group. These are pilot or preliminary data that may support a future randomized trial which would have a separate IRB approval.

- g. Definition of treatment failure or participant removal criteria.

Participants who are not eligible or who are noncompliant with study tasks will be removed from the study early. There are no other early stopping rules in the study.

- h. Description of what happens to participants receiving therapy when study ends or if a participant's participation in the study ends prematurely.

The intervention consists solely of the treatment manual and brief instructions provided at the treatment televisit, and is not accompanied by any ongoing therapy (Sweeney et al., 2019). All participants who complete the treatment televisit will be able to keep their copy of the treatment manual.

5. Inclusion/Exclusion Criteria

Inclusion Criteria

1. Between 18-75 years old
2. Reside in the United States
3. Read, write, and speak English fluently
4. Able to access a video camera on a smartphone, tablet, or other computer
5. Able to receive text messages or emails (or both)
6. Consume greater than or equal to 200 mg caffeine per day in a typical week
7. Indicate a problem that is caused or worsened by caffeine from among the following options: sleep problems, anxiety or nervousness, frequent urination, heartburn or other digestive issues, feel dependent on or addicted to caffeine

8. Interested in getting help to gradually reduce or eliminate caffeine consumption as part of a research study

Exclusion Criteria

1. Evidence of significant depressive symptoms assessed via PROMIS-Depression-8a and medical history
2. Evidence of problematic alcohol use assessed via the AUDIT-C and medical/substance use history
3. Evidence of problematic substance use other than alcohol, nicotine, or caffeine assessed via the DAST-10 and medical/substance use history
4. Evidence of a significant psychiatric disorder, presentation of acute psychiatric symptoms, or any other mental illness that, in the opinion of the investigators, may complicate participation in the study. [Anxiety and sleep disorders are not anticipated to interfere with study participation and will not generally be exclusionary]

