5. Any medical condition that, in the opinion of the investigators, may interfere with or preclude completion of the study

6. Drugs/ Substances/ Devices

- a. The rationale for choosing the drug and dose or for choosing the device to be used.

There are no proposed drugs or devices in the proposed research study.

- b. Justification and safety information if FDA approved drugs will be administered for non-FDA approved indications or if doses or routes of administration or participant populations are changed.

N/A

- c. Justification and safety information if non-FDA approved drugs without an IND will be administered.

N/A

7. Study Statistics

- a. Primary outcome variable.

To determine to what extent participants will engage with a remote caffeine reduction intervention for caffeine-related problems and find it acceptable (*Primary objective*), we will calculate the percentage of completed assessments for each televisit (Treatment, 7 Week Follow-Up, 14 Week Follow-Up) among eligible participants, as well as self-reported agreement with the items on the treatment acceptability survey completed at the 7 Week Follow-Up televisit (e.g., “I read all or most of the Guide to Caffeine Reduction and Cessation,” “Overall, the guide was helpful during my attempt to reduce or quit caffeine.”)

- b. Secondary outcome variables.

To determine to what extent participants are successfully able to reduce their caffeine consumption following the remote intervention (*Secondary objective (a)*), we will assess caffeine consumption as determined by the caffeine surveys at 7-and 14-week post-treatment follow-ups and compare this with consumption at the screening and treatment televisits.

To determine to what extent participants report improvement in common caffeine-related problems (e.g., insomnia, anxiety, gastrointestinal distress) following the remote intervention (*Secondary objective (b)*), we will assess caffeine related problems, anxiety, sleep problems, and gastrointestinal distress via standardized measures (see Table 1) at 7 and 14 weeks post treatment follow-ups and compare this with scores on these assessments at the screening and treatment televisits.

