To determine whether participants randomized to the immediate intervention group show greater caffeine reductions or greater improvements in caffeine-related problems (*Secondary objective (c)*) at the 7-week follow-up relative to the delayed treatment group over the same time-period, we will compare all of the secondary outcome variables described above between the two treatment groups to compare our intervention relative to spontaneous reduction that may occur with the passage of time.

c. Statistical plan including sample size justification and interim data analysis.

Because the primary purpose of this study is to collect pilot and feasibility data rather than determine efficacy via randomized controlled trial, the statistical analysis will be primarily descriptive. Primary outcomes will be reported as the proportion of completed televisits among eligible participants as well as the mean and standard deviation agreement (visual analog scale) with items on the treatment acceptability survey. With respect to secondary outcomes, means and standard deviations for the standardized assessments in Table 1 will be calculated for screening, treatment, 7 Week Follow-Up and 14-Week Follow-Up visits, and we will also visually inspect individual subject data. With respect to comparisons between the immediate and delayed intervention group, we will use a mixed effects regression model with between-subjects factors of group, a within subjects factor of time, and a group x time interaction term. A power analysis indicates that with two groups, four measurements, an alpha of .05, a desired power of .95, correlation among repeated measures of .5, and conservatively estimating a small effect (e.g., partial eta squared = .02), a sample size of 100 will be sufficient to detect a treatment effect. Further, we will calculate Cohen's *d* and partial eta squared effect sizes using means and standard deviations for pre-and post-treatment for all secondary outcomes. These effect size calculations will be used to determine the necessary sample size for any future large-scale randomized controlled trials to assess clinical effects in different treatment populations. The desired sample size of 100 is also based on our laboratory's proven participant capacity for prior randomized clinical trials and long-term human laboratory studies (e.g., Evatt et al., 2016; Sweeney et al., 2017, Sweeney et al., 2019).

d. Early stopping rules.

8. Risks

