Protection against risks of the study procedures: All participants in this study will be thoroughly informed of the potential risks, including of caffeine withdrawal, during the oral informed consent process. Because participation is voluntary, participants can withdraw at any time if they find the behavioral procedures or caffeine withdrawal effects undesirable. The gradual reduction over a period of weeks was specifically designed to reduce the frequency and severity of caffeine withdrawal. The study team carefully reviews medical and social history information from Screening to determine eligibility, and a member of the Behavioral Pharmacology Research Unit (BPRU) medical staff will be consulted if there are medical concerns judged to potentially impact participation.

Protection against risk of a breach in confidentiality: Research staff are highly trained to maintain participant confidentiality. Records and data are maintained on encrypted staff computers and HIPAA-compliant JHMI-credentialed Qualtrics surveys and will only be released outside of the study team with written authorization. Study IDs are used on data collection instruments and in electronic data storage wherever possible in place of any personally identifying information. The identity of subjects is not revealed in written records and documents with subjects' names are shredded before disposal. Televisits will only be arranged via password-protected Zoom meetings with study staff created in the JHMI HIPAA-compliant instance, or through other approved Johns Hopkins Telemedicine Services (e.g., Polycom) in the event of technical or other issues with Zoom. No recordings will be made of participant interactions. Regarding the observer ratings, participants are informed when they identify a community observer of the questions the observer will answer, and that none of the participant's other study information will be shared with the observer and that the observer ratings will not be shared with the participant. Staff have clear instructions to limit the information shared between participant and observer to only that described in the consent form and specified study measures.

c. Plan for reporting unanticipated problems or study deviations.

All unanticipated problems and adverse events will be reported to the IRB and other relevant agencies as required and described in the Data and Safety Monitoring Plan.

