- a. Detail compensation for participants including possible total compensation, proposed bonus, and any proposed reductions or penalties for not completing the protocol.

Participants will not be paid for completing the preliminary screening. Participants will be paid \$20 for the screening televisit, regardless of whether they qualify for subsequent visits. Qualified participants will be paid \$20 for the treatment televisit, \$20 for the Week 7 Follow-Up visit, \$20 for the Week 14 Follow-Up visit, and will be paid \$5 once per week for completing six surveys over six weeks. Participants who complete all of their study televisits will receive a \$50 completion bonus, thus total compensation is anticipated to be \$160 for completed participants. If additional televisits or surveys are necessary, such as in the event of survey or computer error, participants would be paid at the same per-session rate (i.e., \$20 per televisit and \$5 per survey). Compensation will be provided to participants via gift cards (deliverable via postal mail or email), or through creation of the participant as a vendor in the JHU system, where the participant can request a paper check or direct deposit. The payment strategy will depend on the most feasible option available to the study team and/or participant preference. If a participant discontinues caffeine reduction, such as due to adverse effects of caffeine withdrawal, they can still complete study assessments and receive payment and completion bonuses. If participants are withdrawn due to non-compliance or are lost to follow-up they will not receive the completion bonus. Similar to our past research, community observers will not be paid.

11. Costs

- a. Detail costs of study procedure(s) or drug (s) or substance(s) to participants and identify who will pay for them.

There are no costs to participants, although internet/email/video access is an eligibility requirement for participation in the study and the study team will not provide access to the internet or videocamera. The use of zoom or other telemedicine options will be free to participants. All other study costs will be paid for by the research project, which is funded by NIH grant R01DA003890.

References

Bastien, C. H., Vallières, A., & Morin, C. M. (2001). Validation of the Insomnia Severity Index as an outcome measure for insomnia research. *Sleep Medicine*, 2(4), 297-307.

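### Section 4.g ends participation for missed study tasks, which can itself lower the televisit completion that is the primary engagement outcome

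*Combined protocol and SAP*

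**What the plan says.** All references are to the combined protocol and SAP.

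- **Objective (Section 2).** The primary objective is: "Determine to what extent participants will engage with a remote caffeine reduction intervention for caffeine-related problems and find it acceptable".
- **Outcome (Sections 7.a and 7.c).** Engagement is the "percentage of completed assessments for each televisit (Treatment, 7 Week Follow-Up, 14 Week Follow-Up) among eligible participants". Section 7.c words it slightly differently: "Primary outcomes will be reported as the proportion of completed televisits among eligible participants". Both use eligible participants as the denominator.
- **Removal (Section 4.g).** "Participants who are not eligible or who are noncompliant with study tasks will be removed from the study early". The section adds: "There are no other early stopping rules in the study". It does not define noncompliance, and it does not say that a removed person is still offered later visits.
- **Order of events (Section 4.a, Screening Televisit).** "After determining eligibility, participants will be randomized to either the Immediate or Delayed treatment group". Eligibility is therefore settled before anyone can miss a post-randomization task.
- **Other ways out.** Section 8.b gives voluntary withdrawal: "Because participation is voluntary, participants can withdraw at any time if they find the behavioral procedures or caffeine withdrawal effects undesirable". Section 10.a says of people who stop reducing caffeine that "they can still complete study assessments and receive payment and completion bonuses". The same section names withdrawal for noncompliance separately from loss to follow-up and denies the completion bonus in both cases.
- **Acceptability (Sections 4.a, 7.a, 7.c, Table 1).** The survey is given at the Week 7 televisit only and is not repeated at Week 14. It is summarised by mean and standard deviation on a visual analog scale. Nothing is planned for people who do not attend.

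**The concern.** The study wants to know how many people stay engaged, and it measures this by who turns up. A rule under which staff end participation for missed tasks puts a staff decision inside that measurement. Someone removed after earlier missed tasks cannot complete a later televisit even if willing, so completion would partly reflect the rule rather than the participant. Any such person's Week 7 or Week 14 outcome data would be lost as well.

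The acceptability survey has a related limit: people who drop away before Week 7 are never asked, and their view of the guide may differ from that of attenders.

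Section 9.a links larger trials to the intervention proving acceptable and feasible. Completion and acceptability are the two results that speak to this.

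**Working it through.** **1. Which televisits the rule can reach (Section 4.a and Table 1).**

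- *Treatment.* No participant task is scheduled between the Screening and Treatment televisits, in either group. The rule has essentially nothing to act on.
- *Week 7.* Six weekly surveys fall between Treatment and Week 7. Week 7 completion is exposed only if missing them counts as noncompliance, and the plan does not say whether it does.
- *Week 14.* Exposed through a missed Week 7 televisit, or through missed surveys if these count.

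**2. The plan's own figures.**

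- The planned total is 100 (Section 7.c). For the group-by-time test, f² = .02/.98 = 0.0204, and the noncentrality is f² × N × m/(1 − ρ) = 0.0204 × 100 × 4/0.5 = 16.3 on 3 and 294 degrees of freedom. Power is 0.936 against .95 stated. With f rounded up to 0.15, N = 98 is enough. The figure is reproduced to rounding of the effect size. It serves below only as a denominator.
- Payment (Section 10.a): 4 × $20 + 6 × $5 + $50 = $160, as stated.

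**3. Effect on completion, removed participants kept in the denominator.** The documents give no removal, dropout or willingness figures, so these inputs are assumptions: 80 of 100 attend a later televisit, and r of the other 20 were removed by staff, of whom a share q would have attended.

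Understatement in percentage points = r × q, per 100 eligible.

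| r | q = 0 | q = 0.5 | q = 1 |
|---|---|---|---|
| 5 | 0 | 2.5 | 5 |
| 10 | 0 | 5 | 10 |

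Reported completion is 80%; without the rule it would be 80% to 90%. For scale, the Wilson 95% interval for 80/100 is 71.1% to 86.7%.

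**4. Effect if removed participants were dropped from the denominator.** Reported completion becomes 80/(100 − r), against (80 + r × q)/100 without the rule.

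- r = 10: 80/90 = 88.9%, against 80%, 85% or 90% for q = 0, 0.5 or 1. The error is +8.9, +3.9 or −1.1 points.
- r = 5: 80/95 = 84.2%, against 80%, 82.5% or 85%. The error is +4.2, +1.7 or −0.8 points.

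So the direction reverses unless nearly all of those removed would have attended.

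**5. Lost outcome visits.** If removal comes before Week 7, the loss is r × q × 2, which is 0 to 20 of the 200 planned Week 7 and Week 14 visits. If removal follows a missed Week 7 televisit, only Week 14 is lost: r × q, or 0 to 10 of 100.

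**6. Acceptability.** Assumptions: a 0–100 scale, 20% of treated participants not answering, and non-attenders rating g points lower. The mean over all treated is A − 0.2g, where A is the attender mean, so A is too favourable by 0.2g: 0, 2 or 4 points for g = 0, 10 or 20. The error has the same size in the other direction if non-attenders would rate higher. If half of the non-attenders answered by email, the answerers' mean would be A − (10/90)g. The remaining error is 0.2g − 0.111g = 0.089g, or 0.9 and 1.8 points for g = 10 and 20.

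**The case against.** Several counter-arguments have force.

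- *Missed surveys may not trigger removal.* Section 10.a pays each survey separately and ties the bonus to televisits, which fits a missed survey costing only its own fee. A reader might infer that all three televisits are depressed; the documents do not support that. Week 7 is conditional, and Treatment is essentially untouched.
- *Timing is flexible.* Section 4.a sets visits at approximately 7 and 14 weeks, and Section 4.c allows for scheduling. A reader might infer that Week 14 completion can never exceed Week 7 completion. That would need one missed visit to mean permanent removal, which the plan does not state.
- *Staff may remove only people who cannot be reached.* Then nothing is lost. The text does not limit the rule in this way, but it gives no evidence that willing people will be removed either.
- *Persistent noncompliance is itself non-engagement, and an understated completion rate is conservative for a feasibility claim.* This is fair in part. But the outcome is defined as completion of each televisit, and the error is conservative only while removed participants stay in the denominator.
- *The analysis is descriptive with no success threshold, and the middle case (2.5 to 5 points) lies within the sampling interval.* This stands, and it limits the severity.
- *Acceptability.* The plan says openly that the survey belongs to the Week 7 televisit, and Week 7 completion is reported as well, so readers can roughly see whom the mean covers. This stands, so that part of the remedy is optional.

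**Conclusion.** The point holds in a limited form. The noncompliance part of Section 4.g can lower Week 14 completion, can lower Week 7 completion if missed weekly surveys count, and can lose outcome data from removed participants who would have attended. Under the assumptions above, the understatement is 0 to 10 percentage points; the true size cannot be found from the documents and may be zero. The effect is downward or zero as long as removed participants stay among the eligible. The written denominator and the order of eligibility and randomization favour that reading. If they were dropped, the error would generally be upward.

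The acceptability mean describes Week 7 attenders only. Any error from this rests on an assumed scale, non-response rate and rating gap.

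A reader might infer that data from willing participants will certainly be lost, or that the primary outcome is invalid. Neither follows: no removal rate or attendance figure is given, and the study is a mainly descriptive pilot. This is an improvement worth making, with medium confidence in its practical effect.

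**What to change.** **Main change.**

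- In Section 4.g, delete only noncompliance with study tasks as a reason to end follow-up. Leave the part on ineligible participants as it is.
- Keep inviting eligible randomized participants to all remaining assessments unless they withdraw.
- In Sections 7.a and 7.c, state that all of them stay in the completion denominator and that any staff withdrawals are reported separately from loss to follow-up.
- Align the Section 10.a sentence on withdrawal for noncompliance and the completion bonus.

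**Optional.** Email the existing acceptability survey link to treated participants who miss Week 7. Report the number answering out of all treated, with emailed responses identified. Table 1 lists a survey and interview together; the email would cover the survey items only. How many would answer is unknown.

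**Cost.** Wording changes in these sections, some staff time contacting unresponsive participants, and, if the option is taken, mixed-mode collection of the acceptability survey. A participant kept after the Treatment televisit can earn at most 6 × $5 + 2 × $20 + $50 = $120 more, already inside the planned $160. That is at most $600 to $1,200 for 5 to 10 people. Section 10.a does not clearly cover payment for the emailed survey; at the $5 survey rate it would be at most 20 × $5 = $100.
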